7.3 Exclusion Criteria

Patients must be excluded from participating in this study if they meet any of the following criteria:

- (1) Patients with existing ICD or patient having an indication of ICD implantation for secondary prevention of SCD.
- (2) Hospitalisation for HF or for acute coronary syndrome in the previous 40 days.
- (3) Patients where a cardiac resynchronisation therapy (CRT) is planned or indicated
- (4) Other indication for placement of device (sustained ventricular tachycardia, resuscitated sudden death, need for atrioventricular pacing).
- (5) NYHA class I or class IV symptoms at the time of study entry.
- (6) American College of Cardiology-American Heart Association (ACC-AHA) class III or class IV (unstable) angina.
- (7) Patient with chronic renal insufficiency defined as serum creatinine ≥ 3 mg/dl (or ≥ 265.2 μ mol/L).
- (8) Known or suspected hypersensitivity/allergy to Iobenguane or to any of the excipients in AdreView™ (Iobenguane I¹²³ Injection).
- (9) Patient who is pregnant or plans to become pregnant within 2 weeks after AdreView™ (Iobenguane I¹²³ Injection) administration.
- (10) Patient who has used any medication in the 2 weeks before AdreView™ (Iobenguane I¹²³ Injection) that could interfere with the test: e.g., but not limited to amitriptyline or derivatives, imipramine or derivatives, other antidepressants or drugs known or suspected to inhibit the norepinephrine transporter, antihypertensives that deplete norepinephrine stores or inhibit reuptake, sympathomimetic amines or cocaine.
- (11) Patients that have a medical condition that could interfere with the AdreView™ test (e.g., but not limited to left ventricular assist device, or prior heart transplant).
- (12) Patients who participated in a clinical study involving a drug or device within 30 days prior to study entry and patients participating in any other clinical study.
- (13) Patients having serious non-cardiac medical condition associated with significant elevation of plasma catecholamines, including pheochromocytoma.
- (14) Patients with a clinical diagnosis of (or being treated for) Parkinson's disease or Multiple System Atrophy.
- (15) The patient has participated in a research study using ionizing radiation in the previous 12 months.
- (16) Patients previously randomized in this study.

7.4 Withdrawal and Termination Criteria

7.4.1 Patient Withdrawal

There are no formal withdrawal criteria for this study. During the conduct of the study, the Sponsor may review the safety data for trends and signals that would indicate the need for withdrawal of a patient.

In accordance with the Declaration of Helsinki, each patient is free to withdraw from the study at any time. Investigator(s) also have the right to withdraw patients from the study in the event of illness, AEs, or other reasons concerning the health or well-being of the patient, or in the case of lack of co-operation.

Should a patient decide to withdraw after administration of AdreView™, or should the investigator(s) decide to withdraw the patient, all efforts will be made to complete and report the observations up to the time of withdrawal as thoroughly as possible. A complete final evaluation at the time of the patient's withdrawal should be made and an explanation given of why the patient is withdrawing or being withdrawn from the study. As this is an intention to treat analysis, all patients should be followed for the primary endpoint of all-cause mortality if at all possible. ICD crossover or having a secondary endpoint is not a reason to withdraw from the study.

The reason for withdrawal must be noted in the electronic Case Report Form (eCRF). If the reason for withdrawal is a serious adverse event (SAE), monitoring will continue until the outcome is evident. The specific event or test result(s) must be recorded in the eCRF. The reason for withdrawal must be noted in the eCRF. If the reason for withdrawal is a clinical AE, monitoring will continue until the outcome is evident. The specific event or test result(s) must be recorded in the eCRF. Patients withdrawing prior to completing the study may be replaced.

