9.6 End of Study Visit

This will be an event-driven study. Patients will be enrolled and followed up until sufficient endpoints have accrued (247 primary endpoint events). All patients will then attend an end-of-study visit within 1 month.

If a patient discontinues prematurely, he/she will attend an end of study visit at that time. As this is an intention-to-treat analysis, all patients should be followed for the primary endpoint of all-cause mortality if at all possible.

The following parameters will be collected:

- Medical history (with identification of study end-points)
- Concomitant medications
- Vital signs (blood pressure, heart rate, respiratory rate, and pulse oximetry)
- A brief physical examination will be performed.
- AEs, SAEs and AdreView™-emergent AEs
- All data related to primary and secondary endpoints
- ICD interrogation (for those patients with an ICD); may be performed remotely within ±5 days of follow-up visit.

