12.2 Populations for Analysis

A patient is defined as having been included into the study if he/she has met all inclusion criteria, none of the exclusion criteria, and has been assigned to 1 of the enrolment groups (the AdreView™ group or the SoC group). The primary efficacy population is defined as those patients who were randomised to the AdreView™ group or the SoC group.

All randomised patients will be analysed for efficacy in the group to which they were randomised.

The safety population is defined as all patients who were enrolled in the study. All patients will be analysed for safety in the enrolment group to which they were assigned.

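### Section 7.4.1 permits investigators to withdraw randomised patients from the study for illness or AEs, after which most endpoint collection stops, and the SAP then counts such patients as event-free

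*Protocol*

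**What the plan says.** Protocol 7.4.1 opens with "There are no formal withdrawal criteria for this study". It then says "Investigator(s) also have the right to withdraw patients from the study in the event of illness, AEs, or other reasons" related to the patient's health, and adds lack of co-operation as a further ground. For a patient withdrawn after the injection, "all efforts will be made to complete and report the observations up to the time of withdrawal as thoroughly as possible". The section calls the analysis intention to treat and asks that "all patients should be followed for the primary endpoint of all-cause mortality if at all possible". It ends with "Patients withdrawing prior to completing the study may be replaced".

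Two sentences in the same section limit the effect. One is "ICD crossover or having a secondary endpoint is not a reason to withdraw from the study". The other requires an SAE or clinical AE that led to withdrawal to be monitored until its outcome is known.

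Protocol 9.6 adds "If a patient discontinues prematurely, he/she will attend an end of study visit at that time" and repeats the mortality request. Protocol 8.4 says that neither patients nor site staff can be blinded to the arm. Protocol 12.2 says "All randomised patients will be analysed for efficacy in the group to which they were randomised".

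No imputation is planned (Protocol 12.5.3 and 12.11; SAP section 5). SAP 5.4.3 censors event-free patients at the date last known alive for the arrhythmic composite, syncope and the whole-arm device-complication composite. It compares both hospitalisation endpoints and the first key secondary endpoint as proportions, by a CMH test. SAP 5.2 tabulates withdrawals with reasons. Neither document plans a sensitivity analysis for withdrawal.

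**The concern.** AdreView is a diagnostic injection, given once, or twice in AdreView low-risk patients. After the scan there is no continuing study drug to stop, so withdrawing a patient from the study mainly ends data collection. The permitted grounds, illness and AEs, often precede the trial's endpoints, and the person deciding knows the arm. That is how loss of follow-up can become related to outcome and differ between arms.

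In a non-inferiority trial with a margin of 1.20, events missed mainly in the AdreView arm make the claim easier to reach. Ending endpoint collection also runs against the intention-to-treat principle that 7.4.1 itself invokes. And 7.4.1 pulls two ways: illness is a ground for withdrawal and a secondary endpoint is not, yet all-cause hospitalisation is a key secondary endpoint. The text does not say which sentence prevails for a patient hospitalised through illness.

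**Working it through.** **What is still collected after an investigator withdrawal**

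- The AE or SAE that prompted withdrawal: monitored to its outcome (7.4.1).
- Death from any cause: followed on a best-effort basis (7.4.1, 9.6).
- New hospitalisations, arrhythmic events, syncope and device complications: no routine collection, because the end-of-study visit has already taken place.

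**How the SAP treats that patient.** Suppose a patient is withdrawn at month 12 and known to be alive at month 36. For the three endpoints censored at the date last known alive, this patient contributes 36 months at risk with no event, although ascertainment stopped at month 12. In the CMH comparisons the patient counts as having no event, with no stated adjustment for shortened follow-up.

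**The plan's own figures** (Protocol 12.8: one-sided alpha 0.025, power 80%, margin 1.20, assumed HR 0.84, 1:1)

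- Events = 4 × (1.960 + 0.842)² / [ln(0.84/1.20)]² = 246.8, so 247. Reproduced.
- N = 246.79 / [(0.1134 + 0.1333)/2] = 246.79 / 0.12335 = 2000.7, so 2001. Reproduced.
- Screening: 2001/0.85 = 2354. The only inflation is for screen failure; there is no allowance for withdrawal.

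**Non-informative loss.** The documents give no withdrawal rate, so 2%, 5% and 10% are assumptions. If these shares gave no mortality data, 2001 × (1 − share) × 0.12335 gives about 242, 234 or 222 deaths, with power of 79.2%, 78.0% or 75.7%. Because the trial runs to 247 events, this mainly costs time.

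**Informative loss**

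- SE of log HR = 2/√247 = 0.1273.
- Largest observed HR that passes = 1.20 × exp(−1.96 × 0.1273) = 0.935.
- Let f be the share of AdreView deaths missed and g the share of AdreView person-time lost, with SoC follow-up complete. The HR is multiplied by about k = (1 − f)/(1 − g).
- At a true HR of 1.20, one-sided error = Φ(−ln k / 0.1273 − 1.96).

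| f | g | k | Apparent HR | One-sided error |
|---|---|---|---|---|
| 0 | 0 | 1.000 | 1.200 | 2.5% |
| 5% | 0 | 0.950 | 1.140 | 6.0% |
| 10% | 0 | 0.900 | 1.080 | 12.9% |
| 5% | 2.5% | 0.974 | 1.169 | 4.0% |
| 10% | 5% | 0.947 | 1.137 | 6.2% |

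For a given f, the rows with g = 0 are the upper bound: almost only patients about to die are withdrawn. The last two rows assume that withdrawn patients have twice the average hazard, so g = f/2.

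**Opposite direction.** If 5% of SoC deaths alone were missed with no person-time lost, the assumed HR of 0.84 would appear as 0.84/0.95 = 0.884. Power would be Φ(ln(1.20/0.884)/0.1273 − 1.96), about 67% instead of 80%. Equal proportional loss in both arms cancels in the HR.

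**The case against.** The strongest reply is that 7.4.1 already contains safeguards. A secondary endpoint is not a reason to withdraw, and hospitalisation, the arrhythmic composite and syncope are all secondary endpoints, so many worsening patients are covered. The triggering AE is monitored to its outcome, and if that outcome is death it should be captured. Protocol 10.2.11 asks for all AEs to be followed to a final outcome until the end of follow-up. Mortality follow-up is requested twice. Protocol 9.4 also provides for worsening patients inside the study.

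Much of this stands, and it rules out saying that all non-fatal follow-up is lost. It does not close the gap. The bar conflicts with the illness and AE grounds without an order of precedence, and it does not reach a patient who is deteriorating but has not yet had an endpoint. AE monitoring covers the event behind the withdrawal, not new ones.

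Two stronger readings are tempting. A reader might infer that the sickest patients do leave follow-up. The text permits this; nothing in the documents shows that it happens, or in which arm. SoC patients with device complications could equally be withdrawn, which would work against non-inferiority. A reader might also infer that replacement breaks the randomisation by placing a newcomer in the vacated arm. The documents do not support that. Allocation is central through the IWRS and numbers cannot be reassigned (8.2), and randomisation is 1:1 within centre (9.2). The natural reading is that another patient is enrolled and randomised.

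Finally, the SAP records that the sponsor ended the study early (2.4) and reports secondary endpoints for reference only (5.4.4). The 247-event figures therefore describe the planned design, not the analysis now intended.

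**Conclusion.** The concern holds as a defect in the follow-up rules and the matching censoring rules. Followed as written, they permit outcome-related loss of endpoint data, decided by people who know the arm. They also let the SAP treat unobserved time as event-free for the arrhythmic composite, syncope and the whole-arm device-complication composite.

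The size cannot be fixed, because no withdrawal rate is stated. For the planned 247 deaths at a true HR of 1.20, missing 5% (10%) of AdreView deaths alone gives a one-sided error of at most about 6% (13%), or about 4% (6%) at twice the average hazard. These figures assume complete SoC follow-up. Loss confined to SoC would cost power instead, and equal loss would leave the HR about unchanged.

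Replacement is not the source of bias: 12.2 keeps every withdrawn patient in the analysis, so replacement removes nobody and repairs nothing. This is a cheap and worthwhile improvement, not proof of a biased result.

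**What to change.** In Protocol 7.4.1 and 9.6:

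1. Limit investigator withdrawal to stopping the remaining study procedures, such as a scan, with follow-up continuing. Reconcile the illness and AE grounds with the sentence on secondary endpoints. This concerns data collection only and leaves clinical care to the investigator.
2. For every randomised patient, injected or not, keep collecting vital status and all adjudicated endpoints by visit, telephone or records to the common study end, unless the patient withdraws consent to data collection.
3. Delete the replacement sentence as redundant.

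In SAP 5.4.3, censor non-fatal endpoints at the last endpoint assessment, not at the date last known alive. A sensitivity analysis by arm and reason for withdrawal would complete this.

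The cost is wording, plus some telephone or record follow-up of patients who stop visits. No extra patients are needed.

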7.4.2 Study or Site Termination

The DSMB may recommend to the ESC an early termination of the study based upon their review of the safety signals. This board will meet at pre-defined intervals. Any recommendation for an early termination will be promptly communicated to the ESC that will evaluate the report and evidence provided by the DSMB. In the case that this recommendation is not supported by the ESC, both committees will meet to reach a final definitive conclusion. The ESC will have the final say. Once a final opinion is endorsed by the ESC, it is communicated without delay to the Sponsor that will take appropriate action.

This is an event-driven study and the ESC can propose to terminate the study early if sufficient events (as calculated prospectively in this protocol) are reached before the expected end of the study. Similarly, the ESC can propose to terminate the study early if it is unlikely that a sufficient number of events (as calculated prospectively in this protocol) will be reached before the expected end of the study. Finally, the ESC can propose to prolong the study if it is unlikely that a sufficient number of events (as calculated prospectively in this protocol) will be

reached before the expected end of the study but could be reached through an extension that the ESC deems reasonable.

The Sponsor reserves the right to terminate the study at any time. The Sponsor also reserves the right to discontinue participation of a study site at which no patients have been enrolled within 3 months of site initiation or in case of safety concerns or severe protocol violations.

8 TREATMENT OF PATIENTS

8.1 Investigational Medicinal Product (IMP)

8.1.1 AdreView™ (Iobenguane I¹²³ Injection)

After randomisation to either the AdreView™ group or the SoC group, all patients will receive at least one intravenous injection of 10 mCi (370 MBq) of AdreView™. A $\pm 10\%$ tolerance of the nominal dose will be allowed, thus yielding an acceptable dose range of 9 to 11 mCi (333 to 407 MBq) in accordance with the Package Insert/Summary of Product Characteristics/Investigator's Brochure (IB). AdreView™ will be administered in a volume of 5 mL (diluted using 0.9% sodium chloride as needed) and injected as a slow infusion over 1 to 2 minutes followed by 10 mL of saline flush injected over a maximum of 5 seconds. An administration volume of up to 15 mL may be used at sites where there are logistical limitations to achieving delivery of IMP within the timelines required to meet the $370 \pm 10\%$ MBq dose in a volume of 5 mL.

Patients being allocated to the AdreView™ low-risk group will receive a second injection of AdreView™ and planar /SPECT imaging 2 years (± 30 days) after the first one. If any of these patients voluntarily withdraw prior to completion of the study they will be offered this second AdreView™ scan prior to withdrawal being effective.

Refer to the Package Insert/Summary of Product Characteristics/IB and Appendix [15.2](#) for further detail.

8.1.2 Adjunctive Medication: Thyroid Blockade

Thyroid blocking should be performed before administration of AdreView™ in accordance with the Package Insert/Summary of Product Characteristics/IB and local regulations unless the patient has had a complete thyroidectomy.

Each investigator is responsible for obtaining the appropriate thyroid blockade agent and for its administration in accordance with national and local regulations and guidelines. The type of thyroid blockade agent, time of administration, and quantity of compound will be recorded in the eCRF.

8.1.3 AdreView™ Accountability

Each investigator is responsible for ensuring that deliveries of AdreView™ and other study materials from the Sponsor are correctly received, recorded, handled, and stored safely and properly in accordance with all applicable regulatory guidelines, and used in accordance with this protocol.

All AdreView™ containers (opened, unopened, or empty) must be returned to the Sponsor or destroyed on site after the study and overall drug accountability have been completed by the Sponsor or representative. A list of AdreView™ doses and other materials that were returned, or destroyed, must be prepared and signed by the principal investigator or designee. If there are any discrepancies, an explanation for these should also be provided.

8.1.4 Comparator

No comparator imaging modality(ies) will be used. The main comparator will be medical SoC as described in Section [6.1](#).

8.1.5 Registration of Investigational Medicinal Product Complaints

In the event of AdreView™ complaint (e.g., breakage, leakage, particulate matter, discolouration), the investigator or recipient of AdreView™ is requested to report the problem on the AdreView™ shipping documentation (e.g., 'Delivery Note for Product', Drug Shipping and Receiving Form, or equivalent form). This should be promptly forwarded to the person indicated on the shipping documentation. Once received, the Clinical Supplies Manager will register the complaint and determine if the complaint is minor or significant according to Sponsor procedures. All complaints will be followed-up and the appropriate action will be implemented according to Sponsor procedures.

8.2 Method of Numbering Patients and Assigning Patients to Treatment Groups

A unique allocation number will be assigned to each patient in successive order of entering the study after signing the informed consent document at each centre. Patients who fail one or more inclusion/exclusion criteria may be re-screened at a later date and, if subsequently found to be eligible, randomized into the study. No patient may be randomized into the study more than once (i.e., patients withdrawn after randomization may not be re-screened). The allocation number will be unique for each patient in the study and will consist of 7 numbers in total: 3 numbers for the centre identification and 4 numbers for the patient identification at the centre (e.g., 0020001: first patient in centre No. 2). Please see the section on randomisation, Section [9.2](#).

Once an allocation number is assigned, it cannot be reassigned even if the patient is deemed ineligible or withdraws consent. To preserve the scientific integrity of the study, numbers must be assigned in numeric order.

Patients enrolled in the trial will be randomly assigned to the AdreView™ group (will receive AdreView™) or the SoC group (will receive AdreView™, however the results must remain blinded to the investigator). Allocation to the enrolment groups, including randomization, will be performed centrally (via an interactive web response system [IWRS]) by the Sponsor or contract research organisation (CRO).

No patient will be administered AdreView™ before it has been determined that the patient meets the study's inclusion/exclusion criteria and a signed and dated informed consent has been obtained.

8.3 Selection of Doses and Timing

All patients will receive at least one intravenous injection of 10 mCi (370 MBq) of AdreView™. A $\pm 10\%$ tolerance of the nominal dose will be allowed, thus yielding an acceptable dose range of 9 to 11 mCi (333 to 407 MBq) in accordance with the Package Insert/Summary of Product Characteristics/IB (refer to Section 8.1).

AdreView™ will be administered in a volume of 5 mL (diluted using 0.9% sodium chloride as needed) and injected as a slow infusion over 1 to 2 minutes followed by 10 mL of saline flush injected over a maximum of 5 seconds. An administration volume of up to 15 mL may be used at sites where there are logistical limitations to achieving delivery of IMP within the timelines required to meet the $370 \pm 10\%$ MBq dose in a volume of 5 mL.

Patients allocated to the AdreView™ low-risk group will receive a second injection of AdreView™ 2 years (± 30 days) after the first one. Should the H/M ratio from the second scan fall under 1.6 and the patient is willing and eligible for ICD implantation, he/she could receive an ICD. If any of these patients voluntarily withdraw prior to completion of the study they will be offered this second AdreView™ scan prior to withdrawal being effective.

AdreView™ doses and imaging times have been selected following clinical experience and technical information approved by the Health Authorities in the USA and Europe.

8.4 Blinding and Measures to Minimise Bias

Neither patients nor site personnel (including the on-site AdreView™ scan reviewer) can be blinded to group assignment. Sites must know whether patients are randomised to the AdreView™ or SoC groups in order to use the results of the scans in the AdreView™ group. For patients in the randomised SoC group the investigator will remain blinded to the results of the AdreView™ scan.

Both the DSMB and the CEAC will review patient data while blinded to enrolment group. The DSMB could, should it be regarded as necessary for their analysis, also review patient data in an unblinded fashion.

8.5 Prior and Concurrent Therapy

Any medications taken by the patient within 30 days before and up to the end of study visit will be recorded in the eCRF along with the indication and dosage, including but not restricted to guideline-directed optimal medical therapy. Either the generic or the trade name may be recorded. The Sponsor/CRO will encode all therapy and medication according to a current well-recognised dictionary of medical codes.

Should any patients not be receiving guideline-directed optimal medical therapy at target dose per local guidelines, the investigator must document the reason(s) why in the source documents.

As stated in the exclusion criteria, patients will not be allowed to take any medications known or suspected to interfere with AdreView™ imaging as per Package Insert (or Summary of Product Characteristics or IB as applicable) for at least 5 half-lives prior to administration of AdreView™. The investigator will be responsible for assessing the patient's medication in order to determine whether the medication should be withdrawn for the required period. In the case of a patient requiring medications that can interfere with AdreView™ imaging and where the clinical status does not allow temporary withdrawal of the medication, the investigator may elect to withdraw the patient from the study on safety grounds.

